If after a diagnostic interview and a review of available medical records, the potential participant appears to be eligible for the study, he or she will be offered admission into the study. The consent form will contain a detailed description of all study procedures and possible risks and benefits of participation. [name] or a trained research staff person will review the content of the form with the participant and will respond to any questions or concerns. The random assignment to cognitive remediation with tDCS or sham will be explained to participants. To ensure comprehension of the information provided in the consent form, participants will be asked a series of questions to assess their understanding.

Assessment. The assessment schedule is summarized in Table 1. The instruments administered at each assessment point are described below. The screening session will be 2 hours in length. Baseline, post-intervention, and follow up assessments will take approximately 5 hours to complete and will be divided into two 2 ½ hour sessions. Participants will be paid for their participation in all assessment sessions at a rate of \$15/hour.

Diagnostic Screening Assessment (120 minutes). DSM-5 diagnosis will be established with the Structured Clinical Interview for Axis I Disorders (SCID-I) (66). Mood, psychosis, and substance use sections will be

administered. Participant self-report and available medical records will inform these ratings. As part of the diagnostic assessment, a psychosocial, medical, and psychiatric history interview will be completed. To ensure study eligibility, the Test of Premorbid Functioning (67) will be administered to obtain an estimate of premorbid intellectual ability. Last, a tDCS safety screen will be administered to identify existing medical conditions that are incompatible with tDCS (68)(115).

Assessment Instrument	Time				
	Screening Interview	Baseline	2 nd Baseline	Post-Intervention (4-months)	6-wk Follow Up (5.5 months)
SCID-I/DSM-5 conversion	X				
Demographic Interview	X				
Test of Premorbid Functioning	X				
TDCS Safety Screen	X				
Number and Picture N-Back Tasks		X	X	X	X
Rotation and Reading Complex Span Tasks		X	X	X	X
Dot Pattern Expectancy Task		X	X	X	X
AX-Continuous Performance Task		X	X	X	X
Change Detection Task		X	X	X	X
Change Localization Task		X	X	X	X
MATRICS Consensus Cognitive Battery		X	X	X	X
University of California Performance-Based Skills Assessment-Brief		X	X	X	X

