Complex Span task. This task requires both memory storage and a manipulation processing requirement (74). Each trial starts with a memory item that is presented at the center of the computer screen for 500 ms. The memory items are followed by a distracter, presented in the center of the computer screen. The participant is asked to make a decision about the distracter (processing requirement) as quickly and accurately as possible. The distracter disappears after the participant's response, and the next memory item appears. After a few memory–decision sequences, participants are asked to recall the memoranda in correct serial order. The number of memory–decision sequences increases with each trial. Test-retest reliability has been reported to range from (ICC = .71-.90) across versions of the task (75). Performance is based upon the proportion of list elements recalled in correct serial order across trials.

Two adaptable versions of the complex span task will be used as training tasks in the clinical trial. Novel versions of these tasks will be administered in the assessment sessions so that transfer to novel versions of training tasks can be measured as well as impact of the intervention on the interference control component of working memory.

Dot Pattern Expectancy Task. This task was created to assess context processing deficits in patients with schizophrenia and is recognized as a measure of goal maintenance (76). In this continuous performance test the participant views a series of dot patterns that are presented sequentially in the middle of the computer screen. Participants must decide whether each stimulus is a target or a non-target, depending upon whether it was presented immediately after a to-be-remembered stimulus. The task has been found to have good internal consistency (alpha .70-.97), little exposure to ceiling effects, and good retest reliability (77). Performance will be assessed with d prime, a measure of sensitivity.

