AX-Continuous Performance Task. This task is recognized as a measure of goal maintenance (106). In this continuous performance test, the participant views a series of letters that are presented sequentially in the middle of the computer screen. Participants must decide whether each stimulus is a target or non-target, depending upon whether it was presented immediately after a to-be-remember stimulus. This task is highly correlated with the Dot Pattern Expectancy Task ($r = .65$) but is easier to complete (107). Both tasks have been shortened and a composite measure will be made by combining d prime scores on these tasks into a single indicator of goal maintenance performance.

Change Detection Task. (78) In this task, a sample array of colored objects is presented to participants on a computer screen for 200 ms. After a 1,000 ms delay, a test array of colored objects is presented for 3000 ms. On 50% of the trials, the color of one of the items has changed between sample and test arrays. Participants are asked to indicate whether the sample and test arrays are the same or different. Performance across trials is measured with proportion correct, an index of the number of items that have been stored in working memory.

Change Localization Task. (79) In this task, a 5-item array of colored squares were equally spaced around an imaginary circle at the center of the screen. The array is presented for 500 ms. After a 1000 ms delay, the encoding array is followed by a test array. Participants use a mouse to click on the item that has changed to a different color. Performance across trials is measured with the proportion correct and is a measure of working memory capacity. Performance on change detection and localization tasks will be averaged to obtain the working memory capacity measure.

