Study Blinds. To maximize the interpretability of any group differences that occur between the tDCS and sham conditions, multiple blinds will be in place. To equalize expectancy effects, patients will be blind to condition assignment. The StarStim neuromodulator will be used with all participants and is capable of offering a sham stimulation experience that is indistinguishable from tDCS. In addition, to minimize demand characteristics and differential provision of treatment, the interventionists who provide cognitive remediation will be blind to participant condition (tDCS vs sham). Furthermore, steps will be taken to blind the psychology technician who conducts the outcome assessments. Participants will be asked not to describe the intervention they are receiving to the psychology technician. In addition, the technician who conducts the outcome assessments will not provide the clinical intervention. The data collected will be coded in such a way that the investigator who conducts the data analysis will be blind to group membership.

Statistical Analysis Plan. T-tests will be conducted to determine whether important baseline variables are matched, such as working memory performance (N-back performance) and age. If any between-group differences emerge on these factors and they are found to relate to the dependent variables in any of the planned comparisons described below, the confounding variable will be added as a covariate of non-interest in the analysis.

Data Reduction: Consistent with recommendations that change in cognitive function be assessed with multiple measures of the construct (19), each working memory component will be assessed with two measures. Composite scores will be created by averaging the two measures of each aspect of working memory. Composite novel N-Back and novel complex span variables will represent performance on procedurally similar working

memory tasks with novel stimuli, composite scores on capacity, interference control, and goal maintenance tasks will reflect near transfer on untrained working memory measures, the MCCB Speed of Processing and Problem Solving and Reasoning composite will reflect far transfer to a related cognitive domain. Transfer to functional capacity and community functioning will be measured with performance on the UPSA-B Total score and the FE-SFS Total score. Impact on symptom severity will be assessed with the BPRS Total score and the BNSS Total score.

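### Interference control is a primary outcome labelled as untrained near transfer, but the plan's task descriptions point to novel versions of complex span, a procedure trained in every session

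*Combined protocol and SAP*

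**What the plan says.** The plan separates two tiers of working memory outcome: novel versions of the trained tasks, and untrained measures that show near transfer. Specific Aim 1 lists them as (a) and (b), with interference control under (b). In the SAP, Data Reduction repeats the split: "Composite novel N-Back and novel complex span variables will represent performance on procedurally similar working" memory tasks with new stimuli, whereas "composite scores on capacity, interference control, and goal maintenance tasks will reflect near transfer on untrained working memory measures". It also states that "each working memory component will be assessed with two measures", averaged into a composite.

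The Data Analysis Plan for Aims 1 and 2 makes the three components the primary cognitive outcomes. Its reason is that an intervention cannot be called cognitively enhancing unless near transfer is shown. It asks separately for improvement on the UPSA-B.

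On which tasks belong where:

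- Change Localization Task: "Performance on change detection and localization tasks will be averaged to obtain the working memory capacity measure".
- AX-Continuous Performance Task: the composite is made by "combining d prime scores on these tasks into a single indicator of goal maintenance performance", meaning this task and the Dot Pattern Expectancy Task.
- Complex Span task: "Two adaptable versions of the complex span task will be used as training tasks in the clinical trial". The novel versions used at assessment measure transfer to new versions of the training tasks "as well as impact of the intervention on the interference control component of working memory".
- Table 1 schedules "Rotation and Reading Complex Span Tasks" at both baselines, post-intervention and follow-up.
- Integration of Cognitive Training and TDCS: N-back and complex span are practised in every session and are always the tasks paired with stimulation or sham.

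**The concern.** A primary outcome carries a label that the plan's own task descriptions do not support. If interference control is measured by complex span, its procedure is a trained one, and the same scores appear to serve two tiers that the plan treats as distinct. The near-transfer claim is the stated reason for choosing these primary outcomes. At stake is whether a result specific to one trained task format could be presented as evidence that working memory improved on tasks the participants had not practised.

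**Working it through.** The documents give no figure to reproduce, so the check sets the sections side by side.

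**1. Which tasks make up each composite**

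| Component | Two measures | Basis | Named as a trained procedure? |
|---|---|---|---|
| Capacity | Change Detection, Change Localization | Stated | No |
| Goal maintenance | Dot Pattern Expectancy, AX-CPT | Stated | No |
| Interference control | Rotation and Reading complex span | Component link stated; membership inferred | Yes |

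The inference rests on three facts. Two measures per component are required. Complex span is the only instrument linked to interference control anywhere in the documents. Table 1 supplies exactly two complex span tasks. The only other working memory tasks left unassigned in Table 1 are the N-back tasks, which are also trained, so using them would not rescue the label. The plan uses the MCCB only for processing speed and reasoning, as far transfer.

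**2. Count**

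3 composites x 2 measures = 6 near-transfer tasks. Of these, 2 of 6 tasks, and 1 of 3 composites, use a trained procedure.

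**3. Overlap of the tiers**

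Data Reduction puts novel complex span in the procedurally similar tier. If interference control is the average of Rotation and Reading, the same two scores also enter the untrained tier. A complex span result reported under Aim 1a and again under Aim 1b would be one set of data shown twice.

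**4. What the Group x Time test removes**

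For a given composite, let g be the training gain common to both arms, w the effect of tDCS on the working memory component itself, and s the effect of tDCS confined to the complex span format.

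- Interference control: tDCS change minus sham change = (g + w + s) - g = w + s.
- Capacity and goal maintenance: (g + w) - g = w, each composite with its own g and w.

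If w = 0 throughout and s > 0, the three between-arm differences are s, 0 and 0. Randomisation and the sham arm remove g but not s. A significant interaction on interference control therefore cannot by itself separate w from s.

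**5. Size of the risk**

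The documents give no sample size, alpha, standard deviation or effect size, and nothing from which to estimate s. The chance of a misattributed result cannot be calculated from them.

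**The case against.** The strongest defence has four parts.

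- **The dual role is disclosed.** The Complex Span section openly says the novel versions serve both purposes. This stands, but disclosure does not make the untrained label accurate.
- **The plan's definition of near transfer is broad.** The Background accepts new stimuli, new procedures, or both, so new stimuli alone might be thought enough. This softens the point. Yet the same sentence still requires an untrained task, and the plan keeps novel versions of trained tasks in a tier of their own.
- **The assessed tasks are not the trained ones.** They are novel versions, and the trained versions are not described. The shared store-and-process format is clear, but how far memoranda or distracter decisions overlap is not stated. This stands. A reader might infer that the primary outcome simply is a training task; the documents do not support that.
- **Capacity and goal maintenance are clean only by silence.** About 15 training exercises are mentioned, and only N-back and complex span are identified in the text. This also stands, and the comparison depends on the sponsor confirming it.

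The Background does mention gains on training tasks without transfer, and a tDCS gain measured on a training task. A reader might take these as precedents. They concern the training tasks themselves, not novel versions, so they do not show that the feared pattern will occur. The plan also says that N-back and complex span training have each been found to generalise.

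**Conclusion.** The contradiction in labelling holds and should be corrected. On the inferred membership, 1 of 3 primary cognitive composites is described as untrained although it uses a procedure practised in every session during stimulation or sham. Under the plan as written, a tDCS gain specific to that format could be reported as near transfer on an untrained measure.

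This rests on two assumptions: that interference control is the two complex span tasks, and that no unnamed exercise uses a capacity or goal-maintenance procedure. Confidence is high for the contradiction in the text and lower for how likely the consequence is, since the overlap between novel and trained versions is unknown.

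Two stronger readings are not supported. A reader might infer that the plan lets one composite suffice; it does not say so, nor does it say how many are needed. A reader might also infer that trial success turns on this; the separate UPSA-B condition limits the effect on the overall claim of cognitive enhancement. How many primary composites must succeed, and how multiplicity is handled across all primaries including the UPSA-B, is a different issue and not part of this point.

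**What to change.** By dated amendment before unblinding:

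1. Name the two tasks in each composite. If interference control uses other tasks, naming them may settle the matter. At the same time, confirm that no training exercise uses a capacity or goal-maintenance task procedure.
2. If interference control is complex span, describe it in Specific Aim 1, Data Reduction and the Data Analysis Plan as novel versions of a trained procedure. The sponsor should restate whether it stays primary and why, because near transfer is the only reason now given.
3. State that a Group x Time effect on interference control alone will not be reported as near transfer to untrained tasks, and that such a claim must be supported by the capacity and/or goal maintenance composites.
4. If complex span scores are reported under both Aim 1a and Aim 1b, identify them as the same data.

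This needs no new data or visits. The cost is an amendment to how a primary outcome is interpreted, and near transfer on untrained tasks would then rest on two of the three components the plan set out to cover.

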Transcranial Direct Current Stimulation: TDCS will be administered with a StarStim neuromodulator. This device has been approved for use in research with an investigational device exemption due to meeting criteria for non-significant risk. Following the same procedures as were used during our pilot work, the current will be administered at 1 mA via two saline soaked electrode sponges (5 x 7 cm) for 20 minutes. The electrode placement will be based on the 10/20 EEG system. Specifically, the anodal electrode will be placed over F3 (left dorsal lateral prefrontal cortex) and the cathodal electrode will be placed in the contralateral supraorbital position. The neuromodulator can be programmed to offer tDCS or sham stimulation based upon a participant identification number that is programmed into the device. Thus, the device will administer either tDCS or sham stimulation, depending upon condition assignment, and neither the interventionist nor the participants will know the individual's assignment. Participants who are in the sham condition will receive 30 seconds of stimulation at the beginning of the session to mimic the experience of tDCS. This protocol has been found to be effective and is the recommended protocol for blinded tDCS administration (85).

Integration of Cognitive Training and TDCS. Adaptive versions of two integrative working memory tasks, the N-back and complex span tasks, will be trained on during every session. These tasks will be completed at the beginning of each session and will always be the training tasks used concurrent with tDCS or sham stimulation. These tasks were selected for training in conjunction with stimulation because: 1) they require the coordinated use of multiple working memory components, 2) have each been found to produce generalization, and 3) make independent contributions to the prediction of intelligence, suggesting a strong relationship with other higher order cognitive functions (72).

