Data Analysis Plan for Aims 1 and 2: Cognitive and functional improvements are considered equally important outcomes for interventions targeting cognition (64). The primary measures of cognitive outcome for this study will be the capacity, interference control, and goal maintenance composites. These variables were selected as the primary outcomes, as near transfer must be demonstrated for an intervention to be deemed cognitively enhancing (19). The measure of functional capacity, the UPSA-B Total score, will be the primary functional outcome. This is consistent with the NIMH criterion that improvement on a measure of functional capacity must be demonstrated in addition to cognitive improvement for an intervention to be classified as cognitively enhancing (86). Thus, near transfer and change in functional capacity are the outcomes that have been deemed to be clinically meaningful. Mixed model approaches will be used, as they are well-suited to examining within subject change over time.

Specific Aim 1: Near and Far Transfer of Training. Mixed effect, repeated measure ANOVAs will be completed to test the hypotheses that WMT and tDCS will enhance performance significantly more than WMT and sham on 1) novel versions of trained tasks, 2) untrained working memory measures, 3) measure of related cognitive functions, 4) functional capacity, and 5) community functioning. Symptom severity is predicted to improve significantly more with WMT and tDCS than WMT and sham. Significant Group x Time interactions will allow rejection of the null hypothesis that WMT + tDCS offers no benefit as compared to sham.

Specific Aim 2: Durability of Cognitive and Functional Changes. To examine durability of near and far transfer and symptom change, mixed model repeated measure ANOVAs will be conducted. TDCS-induced cognitive change is expected to endure and post-intervention between group differences maintained.

References

2. Gold JM. Cognitive deficits as treatment targets in schizophrenia. *Schizophr Res*. 2004;72(1):21-8.

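### Three primary near-transfer composites share one no-benefit null, but the plan gives no alpha, adjustment or success rule; if any one suffices, false findings favouring tDCS run at 5.5–7.3% instead of 2.5%

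*Combined protocol and SAP*

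**What the plan says.** The Data Analysis Plan for Aims 1 and 2 sets the primary cognitive outcomes: "The primary measures of cognitive outcome for this study will be the capacity, interference control, and goal maintenance composites". It justifies them on the ground that "near transfer must be demonstrated for an intervention to be deemed cognitively enhancing". The UPSA-B total is the primary functional outcome. That choice is supported by an external criterion under which "improvement on a measure of functional capacity must be demonstrated in addition to cognitive improvement".

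The only decision sentence is under Specific Aim 1: "Significant Group x Time interactions will allow rejection of the null hypothesis that WMT + tDCS offers no benefit as compared to sham". It follows a list of five outcome classes plus symptom severity. Under Specific Aim 2, "To examine durability of near and far transfer and symptom change, mixed model repeated measure ANOVAs will be conducted". No section gives a significance level, sidedness, adjustment, testing order or rule for combining the three composites.

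Table 1 schedules every outcome at two baselines, post-intervention and 6-week follow-up. Hypothesis 2 and the Aim 2 text both refer to a group difference at post-intervention, which places the Aim 1 comparison there. Neither says which baseline enters the test or which interaction contrast is used.

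On what counts as untrained, Data Reduction says "composite scores on capacity, interference control, and goal maintenance tasks will reflect near transfer on untrained working memory measures". The Complex Span task section says the novel span versions are given "so that transfer to novel versions of training tasks can be measured as well as impact of the intervention on the interference control component". The section on integrating training with tDCS says "Adaptive versions of two integrative working memory tasks, the N-back and complex span tasks, will be trained on during every session".

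**The concern.** Three tests feed one conclusion, and the plan does not say how they combine. The choice between one composite and all three could therefore be made after seeing which are significant. Near transfer is the plan's own condition for calling the intervention cognitively enhancing, so the rule decides what the trial may claim. Readers can apply Holm to reported p-values, but they cannot recover the rule, baseline or contrast that was intended.

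The composites also differ in kind. Interference control appears to rest on variants of a task practised in every session. If any one composite suffices, a gain on that one alone could be reported as transfer to untrained measures.

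**Working it through.** **Inputs.** Three primary composites and one primary functional outcome (Data Analysis Plan). Assumed, because the documents give neither: two-sided 0.05 per test, and equal correlation ρ between test statistics, taken from 0 to 0.9. The only between-task correlation given among these measures is 0.65 (AX-Continuous Performance Task section). It is for two tasks inside the goal maintenance composite, so it serves only as a reference point. The plan has no error-rate, power or sample-size figure to reproduce.

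**Any one of three suffices, none truly improves.** At ρ = 0:

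- either direction: 1 − 0.95³ = 0.1426
- favouring tDCS: 1 − 0.975³ = 0.0731

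For ρ > 0, the rate favouring tDCS is 1 − E[Φ((1.96 − √ρ·X)/√(1−ρ))³] with X standard normal. The two-directional rate replaces Φ by the probability between the two critical values.

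| ρ | Favouring tDCS | Either direction |
|---|---|---|
| 0 | 7.3% | 14.3% |
| 0.5 | 6.3% | 12.5% |
| 0.65 | 5.7% | 11.4% |
| 0.7 | 5.5% | 10.9% |
| 0.9 | 4.2% | 8.4% |
| one test | 2.5% | 5.0% |

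With t tests on 30 or 60 degrees of freedom, or interaction tests with 2 or 3 degrees of freedom, the two-directional rate stays at about 14% (ρ = 0) and 11% (ρ = 0.7).

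**All three required, none truly improves.** Two-sided: 0.05³ ≈ 0.01% at ρ = 0, 0.9% at 0.7, 2.3% at 0.9. There is no inflation.

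**Any one of three, and UPSA-B too.** If nothing works, favouring tDCS: 0.0731 × 0.025 = 0.0018, or 0.2%, at ρ = 0, rising to 2.0% at 0.9. If UPSA-B truly improves and is detected, the near-transfer part returns to the table above.

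**Holm over the three composites** (0.05/3 = 0.0167, then 0.025, then 0.05), counting near transfer to untrained measures only when capacity or goal maintenance is significant in favour of tDCS, for ρ from 0 to 0.9:

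- no composite truly improves: 1.7% down to 1.3%
- only interference control truly improves: 2.5% down to 1.8%

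**Power, illustrative.** 80% power at two-sided 0.05 means a shift of 1.960 + 0.842 = 2.802. The critical value at 0.0167 is 2.394, so power there is Φ(2.802 − 2.394) = Φ(0.408) ≈ 66%. If all three composites have 80% power, Holm with capacity or goal maintenance required passes 91 / 83 / 79 / 74% at ρ = 0 / 0.5 / 0.7 / 0.9. Adding UPSA-B, also at 80%, gives about 71–72% throughout (at ρ = 0, 0.906 × 0.80 = 0.725). All three composites plus UPSA-B gives 41 / 56 / 62 / 70%.

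**Is interference control untrained?** Table 1 lists only two complex span tasks, rotation and reading, and no section assigns another task to interference control. The same tasks therefore appear to serve both as novel versions of trained tasks and as untrained measures, two tiers that Specific Aim 1 and Data Reduction keep apart.

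**The case against.** The hypotheses are directional, and a result favouring sham would not be reported as near transfer. A reader might take 11–14% as the trial's false-positive rate. That is the two-directional figure under one reading of the rule; the relevant rate is the one favouring tDCS. This objection stands.

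The cited criterion asks for functional capacity as well as cognition. If that governs the cognitively enhancing label, the false label when nothing works is 0.2–2.0%, below a single test's 2.5%. This also stands, within limits: the plan uses the criterion to justify its outcomes and does not write it as a rejection rule, it leaves open how the three composites combine, and it gives no protection if UPSA-B truly improves.

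The assessment section says it is unknown whether working memory components differ in malleability, and selects measures so that each can be assessed. Three separate component-level conclusions may therefore be intended, and whether those need joint control is debatable. But the Aim 1 sentence gathers the interactions under one null, so the any-of-three reading remains open.

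A reader might also infer that the plan names no time point. It does point Aim 1 to post-intervention; only the baseline and the contrast are open.

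Finally, the Background definition of near transfer asks for an untrained task with unfamiliar stimuli, procedures, or both. Novel-stimulus span tasks can arguably meet it, so the documents do not show that the classification is simply wrong. They show a tension to be reconciled.

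The analyst is blind to group, which limits choosing a rule by direction but not by significance.

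**Conclusion.** The omission is real and should be fixed. As written, the plan permits an unadjusted any-of-three claim. On that reading, false near-transfer findings favouring tDCS run at 7.3% to 5.5% for correlations 0 to 0.7 (14.3% to 10.9% in either direction), against 2.5% for one test. This rests on an assumed two-sided 0.05, an assumed equal correlation and no true effect on any composite. The documents do not establish that any-of-three is the intended rule, and they do not support saying that the cognitively enhancing label itself carries this error rate. The interference-control classification is a separate, arguable inconsistency that matters most if one composite can carry the claim.

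**What to change.** Before unblinding, add a paragraph to the SAP that:

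1. States two-sided alpha 0.05.
2. Makes the primary test the Group x Time contrast from a named baseline to post-intervention, with Aim 2 tests secondary. The practice-effect rationale in Research Design and Methods points to the second baseline.
3. Tests the three composites with Holm at family-wise 0.05.
4. Reconciles Data Reduction with the Complex Span and training sections, and reports a result resting on interference control alone as transfer to novel versions of a trained task, not to untrained measures.
5. States whether UPSA-B must also be significant before the cognitively enhancing label is used. That is the sponsor's choice.

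No new data are needed. The cost is power: 80% at 0.05 becomes about 66% at the first Holm step, and 90% becomes about 80%. If UPSA-B is also required, joint power is about 71–72% with 80% on each outcome and near transfer judged by Holm with capacity or goal maintenance required. Requiring all three composites instead also controls error, but gives 51–72% before UPSA-B is added. The documents give no power of their own, so these figures only illustrate the trade-off.
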